## LIST OF ABBREVIATIONS

ADA	anti-drug antibodies
AE	adverse event
ALT	alanine aminotransferase
ANA	antinuclear antibody
AST	aspartate aminotransferase
ATC	Anatomical Therapeutic Chemical
AUC 0-24	area under the serum concentration-time curve from pre-dose (time 0) to 24 hours post-dose
AUC 0-∞	area under the serum concentration-time curve from pre-dose (time 0) to infinity
BLQ	below the limit of quantification
BMI	body mass index
BUN	blood urea nitrogen
CAR-T	chimeric antigen receptor and T-cell
CFR	Code of Federal Regulations
C3	complement component 3
CBC	complete blood count
CIC	circulating immune complexes
CLL	chronic lymphocytic leukemia
C max	maximum serum concentration determined directly from the concentration-time profile
CRO	contract research organization
CV	coefficient of variation
D5W	dextrose 5% in water
DAT	direct antiglobulin test
DEC	Dose Escalation Committee
DLT	dose-limiting toxicity
DNA	deoxyribonucleic acid
dsDNA	double-stranded deoxyribonucleic acid
ECG	electrocardiogram
eCRF	electronic case report form
EDC	electronic data capture
eGFR	estimated glomerular filtration rate
ET	early termination
FCGR2A	Fc gamma R2a receptor
FcRn	neonatal Fc receptor
FDA	Food and Drug Administration
GCP	Good Clinical Practice
GI	gastrointestinal
GLP	Good Laboratory Practice

HBV	hepatitis B virus
HCV	hepatitis C virus
HIPAA	Health Insurance Portability and Accountability Act
HIV	human immunodeficiency virus
IB	Investigator's Brochure
IC	immune complex
ICF	informed consent form
ICH	International Council for Harmonisation of Technical Requirements for Pharmaceuticals for Human Use
IgA	immunoglobulin A
IgG	immunoglobulin G
IgM	immunoglobulin M
IND	investigational new drug
IRB	institutional review board
IRR	infusion-related reaction
IUD	intrauterine device
IV	intravenous
IVIG	intravenous immunoglobulin
LDH	lactate dehydrogenase
LLN	lower limit of normal
mAb	monoclonal antibody
MedDRA	Medical Dictionary for Regulatory Activities
NCI CTCAE	National Cancer Institute Common Terminology Criteria for Adverse Events
NHL	non-Hodgkin lymphoma
NHP	non-human primate
NK	natural killer
NOAEL	no-observed-adverse-effect level
NSAID	non-steroidal anti-inflammatory drug
PD	pharmacodynamics
PK	pharmacokinetic
RBC	red blood cells
RNA	ribonucleic acid
RNAseq	RNA sequencing
QTcF	corrected QT interval using Fridericia's formula
SAE	serious adverse event
SAP	statistical analysis plan
SAS	Statistical Analysis System
SD	standard deviation
SNP	single nucleotide polymorphism
SOC	system organ class
SOP	standard operating procedures

SYNT001	a humanized, affinity matured IgG4-kappa monoclonal antibody
$t_{1/2}$	Half-life
TEAE	treatment-emergent adverse event
$T_{max}$	observed time to reach peak serum concentration
ULN	upper limit of normal
UNS	unscheduled
US	United States
VZV	Varicella-Zoster virus
WAIHA	warm autoimmune hemolytic anemia
WHO	World Health Organization
WHO-DD	World Health Organization Drug Dictionary

## 2. BACKGROUND AND RATIONALE

SYNT001, a humanized, affinity-matured IgG4-kappa monoclonal antibody (mAb), blocks immunoglobulin G (IgG) and IgG immune complex (IC) interactions with the neonatal crystallizable fragment receptor (FcRn) and thereby inhibits the varied roles of FcRn in immune response.

Through specific and high affinity blockade of FcRn, SYNT001 has been shown to increase the catabolism of IgG and IgG IC in healthy volunteers and is predicted to block the ability of IgG IC to activate intracellular signaling events associated with binding to FcRn. This predicts that SYNT001 will also accelerate degradation of endogenous circulating IgG autoantibodies and IgG IC specifically involved in the pathogenesis of autoimmunity. Blocking FcRn interactions with IgG ICs further predicts that SYNT001 will have consequences for innate and adaptive cellular immunity. In the first instance, blocking multimeric IgG IC's interactions with FcRn within antigen-presenting cells should result in inhibition of IC-mediated inflammatory cytokine production and release by these cells. In addition, as FcRn determines the intracellular itinerary of IgG ICs within and among compartments important in cellular immunity, it is further anticipated that SYNT001 will block antigen processing and presentation of antigens contained within ICs that would otherwise lead to CD8+ and CD4+ T cell activation. Thus, SYNT001 is expected to specifically target immune functions associated with IgG and IC that are involved in certain IgG-mediated autoimmune conditions.

SYNT001 targets key mechanisms contributing to pathology in a variety of IgG-mediated autoimmune disorders. While current treatments for certain autoimmune disorders, including chronic steroids, immunosuppressants, intravenous (IV) immunoglobulin (IVIG), plasmapheresis, and anti-CD20 mAbs, such as rituximab, can be effective, they are associated with significant adverse effects, and delayed or non-durable responses.

IgG autoantibodies directed against red blood cells (RBCs) are considered to play a central role in the hemolysis and anemia observed in patients with warm autoimmune hemolytic anemia (WAIHA). SYNT001 is a humanized IgG4 mAb that blocks IgG interactions with FcRn that would be anticipated to affect the pathogenic behavior of IgG autoantibodies. Administration of SYNT001 significantly decreases total IgG levels, including a corresponding decrease in the levels of the pathogenic autoantibodies. This may lead to a decrease in the IgG coating of RBCs and the interaction of IgG-coated RBCs with FcRn in phagocytic cells, leading to decreased hemolysis in WAIHA patients with active hemolysis. Moreover, the ability of SYNT001 to reduce circulating immune complexes (CICs) and the associated innate and adaptive immune responses may allow for further sustained disease modification.

### 2.1 Study Rationale

This study is being conducted to evaluate the safety, tolerability, pharmacokinetics (PK), pharmacodynamics (PD), immunogenicity, and effects of IV SYNT001 in subjects with WAIHA.

## 2.2 Selection of Doses in this Study

The initial dose levels of SYNT001 for this Phase 1b/2 proof-of-concept study of 10 mg/kg and up to 30 mg/kg were selected from careful review of the safety, tolerability, and PD effect on total IgG levels after single and repeat dosing of SYNT001 in non-human primates (NHPs), as well as the safety, tolerability, and PD effect on total IgG levels after single ascending doses of SYNT001 in healthy volunteers. In addition, further consideration was given to the desired level of FcRn blockade to achieve suppression of IgG to a range that has been previously correlated with disease remission. Further, we considered the potential effects of inhibiting FcRn function as they relate to immune complex-associated innate and adaptive immunity in choosing these dose levels based upon exploratory studies of a single ascending dose of SYNT001 in healthy volunteers. From the NHP studies, single doses of SYNT001 produced a dose-dependent decrease in total IgG and a further decrease was seen with repeated weekly doses up to a maximum of 70% reduction at 100 mg/kg. This magnitude of total IgG reduction is approaching the expected maximal 90% inhibition of FcRn function based on murine studies also performed by the Sponsor and others (Nixon et al., 2015; Roopenian et al., 2003). In the recently completed Phase 1a trial with SYNT001 in healthy volunteers a single dose caused a maximum average 50% drop in total IgG with IV dosing at 30 mg/kg. Based on the NHP studies, further reductions are expected following multiple dosing. A corresponding decrease in pathogenic autoantibodies is anticipated.

A semi-mechanistic model of FcRn-IgG interactions and FcRn inhibition with SYNT001 was jointly developed by Applied BioMath and the Sponsor. The model was designed to simulate PK and PD responses to various dosing regimens of SYNT001 to inform clinical trial design. Initial simulations were able to capture both PK and PD responses to single doses of SYNT001 from a single-ascending dose study in healthy volunteers and predict multiple dose responses from ongoing studies with good fidelity. The model predicted an IgG reduction of approximately 75% by Day 33, which was determined to be acceptably close to the actual mean IgG reduction of 59% by Day 30 observed in patients. Subsequent iterations of the model have used patient data from ongoing patient studies to further calibrate dose responses. In the most recent simulations, multiple dosing scenarios have been explored, including responses to weekly, bi-weekly, and loading doses. A simulated dosing regimen consisting of three weekly loading doses of 30 mg/kg SYNT001 followed by every other week maintenance doses of 10 mg/kg SYNT001 achieved a nadir IgG reduction of approximately 78% between Days 21 and 28 and maintained an IgG reduction between approximately 50% and 68%. This level of total IgG reduction has been associated with clinical efficacy in early studies of SYNT001-treated pemphigus subjects, and represents a target for future studies in other indications. This regimen of 30 mg/kg loading doses and 10 mg/kg maintenance doses was determined to be the optimal starting regimen to achieve meaningful IgG reduction while maximizing patient safety. Future cohorts may increase the maintenance doses to 20 mg/kg SYNT001, which the model predicts will achieve greater IgG reductions between approximately 55% and 72%. Given the rigorous biological approach taken in the development of the model, simulations of dosing schedules can be considered reliable for the purpose of planning clinical trials.

Several recently completed non-clinical studies support the proposed Cohort 2 dose and dosing regimen. A recently completed 27-week dose-response good laboratory practice (GLP) toxicology study in non-human primates assessed the long-term safety, toxicology, and

toxicokinetics of weekly IV doses of SYNT001. Twenty-seven (27) once weekly 10-minute infusions of SYNT001, at doses of 5, 30, or 100 mg/kg, to cynomolgus monkeys was associated with non-adverse test article-related clinical effects and clinical pathology observations at  $\geq 5$  mg/kg. SYNT001 produced dose-dependent reduction of serum IgG levels without affecting IgA, IgM or albumin levels. The No-Observed Adverse-Effect Level (NOAEL) of SYNT001 was 100 mg/kg following 17 infusions and 30 mg/kg following 27 infusions.

As indicated above, in the recently completed Phase 1a healthy male volunteer study, single doses of SYNT001 up to and including 30 mg/kg have been well tolerated. There were no dose-limiting toxicities (DLTs), serious adverse events (SAEs), or any other safety concerns identified. No adverse events (AEs) were observed in the 1 and 3 mg/kg dose cohorts. The only moderate (Grade 2) AE observed was a single instance of headache in the 10 mg/kg cohort. Other subjects had mild (Grade 1) AEs at 10 mg/kg. In Cohort 4 (30 mg/kg), five subjects received SYNT001. All five subjects experienced AEs; all were mild (Grade 1), transient and resolved spontaneously without intervention.

A preliminary assessment of safety was conducted by SYNT001 Pemphigus Study SYNT001-103 Dose Escalation Committee (DEC). Seven subjects with pemphigus were treated with 10 mg/kg IV weekly doses over a period of 5 weeks. Overall, SYNT001 10 mg/kg IV was well tolerated. Headache (Grade 1 or 2, self-limited) was the only drug-related AE that was reported in more than one subject. Total IgG and CIC biomarkers were reduced by 59% and 50% respectively, from baseline levels following the fifth dose, returning to baseline within 1-2 months. Additionally, preliminary evidence of clinical efficacy as measured by a clinically validated scoring metric, the Pemphigus Disease Area Index, was observed across the population. The DEC approved a dose escalation of SYNT001 from 10 mg/kg IV weekly doses for 5 weeks (Cohort 1) to 30 mg/kg IV weekly doses for 5 weeks (Cohort 2).

Given these preliminary data in non-clinical toxicology species and human subjects, as well as supporting evidence from the computational model, it is anticipated that the doses and dose regimens selected for this study will be well tolerated and will demonstrate clinically relevant pharmacodynamic effects and efficacy in patients with WAIHA. For a summary of findings from the single dose clinical study in healthy subjects and further details regarding the nonclinical findings, please refer to the SYNT001 Investigators Brochure.

### **2.3 Compliance Statement**

This study will be conducted in compliance with Good Clinical Practice (GCP), including the International Council for Harmonisation of Technical Requirements for Pharmaceuticals for Human Use (ICH) Guidelines and Food and Drug Administration (FDA) regulations, consistent with the principles outlined in the Declaration of Helsinki. In addition, the Investigator agrees to adhere to all applicable local laws and regulatory requirements relevant to the use of new therapeutic agents.

The study will be conducted in compliance with the protocol. The appropriate Institutional Review Boards (IRBs) must approve the protocol, any amendments, and the subject informed consent form (ICF) prior to implementation.

Freely given written informed consent must be obtained from every subject prior to participation in this clinical trial. As part of this procedure, the Investigator must explain orally and in writing the nature, duration, and purpose of the study, and the action of the drug in such a manner that the study subject is aware of the potential risks, inconveniences, or AEs that may occur. The study subject should be informed that he/she is free to withdraw from the study at any time. He/she will receive all information that is required by federal regulations and ICH guidelines. The Investigator or designee will provide the Sponsor with a copy of the IRB-approved informed consent form prior to the start of the study. The rights, safety, and well-being of participating subjects are the most important considerations and should prevail over interests of science and society.

Study personnel involved in conducting this trial will be qualified by education, training, and experience to perform their respective task(s). This trial will not use the services of study personnel where sanctions have been invoked or where there has been scientific misconduct or fraud (eg, loss of medical licensure, debarment).

### 3. STUDY OBJECTIVES AND ENDPOINTS

Primary Objective	Primary Endpoint
Safety: To evaluate the safety and tolerability of IV infusions of SYNT001 at different dose levels and dosing regimens in subjects with WAIHA	Safety: The evaluation of SYNT001 safety based on vital signs, physical examinations, electrocardiograms (ECGs), clinical safety laboratory tests, the incidence of AEs, treatment-emergent adverse events (TEAEs), and SAEs summarized by dose and dosing regimen, severity, and relationship to study drug
Secondary Objective	Secondary Endpoint
To evaluate the efficacy of doses of SYNT001 at different dose levels and dosing regimens on PD biomarkers	The evaluation of PD biomarkers based on absolute serum levels and percent change from baseline of total IgG, IgG subtypes (IgG1-4), immunoglobulin A (IgA), immunoglobulin M (IgM), albumin, and CIC summarized by dose, dosing regimen and time point
To determine the PK of SYNT001 following IV infusions at different dose levels and dosing regimens	The determination of PK parameters including half-life ( $t_{1/2}$ ), maximum serum concentration determined directly from the concentration-time profile ( $C_{max}$ ), observed time of peak serum concentration ( $T_{max}$ ), area under the serum concentration-time curve from pre-dose ( $time_0$ ) to 24 hours post-dose ( $AUC_{0-24}$ ), and area under the serum concentration-time curve from pre-dose ( $time_0$ ) to infinity ( $AUC_{0-\infty}$ ), (Cohort 1); maximum serum concentration determined directly from the maximum serum concentration and corresponding $T_{max}$ (Cohort 2) summarized by dose, dosing regimen and time point
To assess the efficacy of doses of SYNT001 at different dose levels and dosing regimens on disease markers	The assessment of WAIHA disease activity by absolute changes in the disease activity markers of hematocrit, hemoglobin, platelet count, reticulocyte count, lactate dehydrogenase (LDH), haptoglobin, and total and indirect bilirubin will be summarized by dose, dosing regimen and time point The direct Coombs test result (positive or negative) will be summarized by dose, dosing regimen and time point
To measure the immunogenicity of SYNT001 administered at different dose levels and dosing regimens	The immunogenicity of SYNT001, as determined by presence of anti-SYNT001 binding antibodies and neutralizing antibodies, summarized by dose, dosing regimen and time point
Exploratory Objectives	Exploratory Endpoint
To explore the effect of SYNT001 at different dose levels and dosing regimens on biomarkers to understand the pathophysiology of the disease	The exploration of SYNT001 mechanisms of action and effects of SYNT001 on pathophysiology summarized by dose, dosing

and the SYNT001 mechanisms of action	regimen and time point, as determined by: 

• D-dimer

• Antiphospholipid antibodies (lupus anticoagulant, anti-cardiolipin antibody, anti-beta-2-GP1 antibody)

• Antinuclear antibody titer

• Anti-double-stranded deoxyribonucleic acid (dsDNA) antibody titer

• Quantitative Coombs assay

• Cold agglutinins (titer and thermal amplitude)

• Fc gamma R2A receptor (FCGR2A) single nucleotide polymorphisms (SNP) by genotyping

• Complement component 3 levels by nephelometry

• Presence of disease and inflammatory markers by total ribonucleic acid (RNA) sequencing

• Immunophenotyping including measurements of T cells, monocytes, natural killer (NK) cells, and B cells by flow cytometry

To characterize blood transfusions during the study	The number of units of packed red blood cells received by subjects will be summarized by dose and dosing regimen
To determine the impact of different SYNT001 dose levels and dosing regimens on the subject's use of corticosteroids to treat their WAIHA	The evaluation of corticosteroid use during the study will be summarized by dose, dosing regimen and time point

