### 5.2 Inclusion Criteria

A subject must meet the following criteria to be eligible for the study:

1. Willing and able to read, understand and sign an informed consent form.
2. Male or female  $\geq 18$  years of age at the time of screening.
3. Confirmed diagnosis by enrolling physician of WAIHA, including positive direct Coombs test.
4. Hemoglobin  $< 11$  g/dL.
5. Evidence of active hemolysis including any one of the below:
  - a. LDH  $>$  upper limit of normal (ULN) or
  - b. Haptoglobin  $<$  lower limit of normal (LLN) or
  - c. Indirect bilirubin  $>$  ULN.
6. Other treatments for WAIHA:
  - a. If treated with rituximab or other anti-CD20 mAb, last dose  $> 3$  months prior to screening (a dose is defined as  $\geq 10\%$  of the intended dose).
  - b. If being treated with other immunosuppressants (ie, azathioprine, mycophenolate mofetil, methotrexate, cyclosporine, tacrolimus, sirolimus, or low-dose oral cyclophosphamide [ $\leq 100$  mg/day]), dose must be stable ( $< 25\%$  change in dose) for the 4 weeks prior to screening.
  - c. If being treated with corticosteroids, dose must be  $\leq 1$  mg/kg/day of prednisone or equivalent, and the dose may not be increased by more than 50% in the 2 weeks prior to screening.
  - d. No pulse corticosteroids are allowed in the 2 weeks prior to screening.
7. Treatment of chronic lymphocyte leukemia (CLL) or non-Hodgkin lymphoma (NHL) must be:
  - a. FDA-approved for oral treatment, and
  - b. Stable ( $< 10\%$  change in dose) for 6 weeks prior to screening; Bruton's tyrosine kinase inhibitor dose must be stable ( $< 10\%$  change in dose) for 8 weeks prior to screening.
8. Body mass index (BMI)  $> 18.5$  kg/m^2.
9. Has a negative pregnancy test (for women of childbearing potential) documented prior to the first dose of study drug.
10. Females of childbearing potential must agree to be abstinent or else use any two of the following medically acceptable forms of contraception ( $< 1\%$  per year failure rate) from the screening period through the final study visit: oral contraceptive, condom with or without spermicidal jelly, diaphragm or cervical cap with spermicidal jelly, or intra-uterine device (IUD). A female whose male partner has had a vasectomy must agree to use one additional form of medically acceptable contraception.

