### **6.7.8 Direct Antiglobulin (Coombs) Test (DAT)**

WAIHA is caused by autoantibodies (usually IgG) that bind to RBC antigens. This results to the activation of the complement system and deposition of complement protein C3 on the RBCs. Red blood cells coated with IgG with or without complement disposition are removed from the circulation by the reticuloendothelial system in the spleen and liver leading to anemia via a process known as extravascular hemolysis. The direct antiglobulin, or Coombs, test is used to determine whether a patient's RBCs are coated with IgG and/or complement proteins. Anti-IgG and anti-C3 antisera are added to a patient's red cells, and if IgG or C3 are present the RBCs clump or agglutinate, which is detected visually.

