### **6.7.9 Quantitative Coombs Assay**

Subject and control RBC-bound IgG, IgM and C3 will be measured by flow cytometry. RBCs coated with serial dilutions of monoclonal anti-Rh(D) IgG and IgM serve as positive controls. Quantum™ MESF (Molecules of Equivalent Soluble Fluorochrome) microsphere beads coated with known numbers of fluorescent dye molecules are used as internal validation markers prior to analysis. Dynabeads® Protein G are used to quantify binding of mouse anti-human IgG, IgM and C3 antibodies. Binding of IgG is expressed as the geometric mean of the fluorescence intensity.

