### 9.6.3 Potential Immune Effects

An antibody blocking FcRn is anticipated to have several effects. These include acceleration of catabolism of IgG, but not other immunoglobulin isotypes such as IgA and IgM, leading to dose-dependent decreases in circulating IgG levels by up to an estimated 50% from the baseline levels

after a single dose and further decreases after multiple doses up to a 70% to 80% reduction. Based on studies in humans, it is expected that with a single dose, the nadir of this effect will occur approximately 5 days after dosing. The time course of recovery of IgG following dosing in the Phase 1a study suggests that a return to within 30% of baseline levels observed at pretreatment occurs within 4 weeks after a single dose and within 4 weeks after multiple doses as shown in NHPs.

Given the normal adult range of total IgG of 500 to 1600 mg/dL ([Agarwal and Cunningham-Rundles, 2007](#); [Furst, 2009](#); [Gonzalez-Quintela et al., 2008](#); [Jolliff et al., 1982](#); [Keystone et al., 2007](#); [McMillan et al., 1997](#); [van Vollenhoven et al., 2013](#)), with a mean of 1150 mg/dL, a 50% decrease in mean total IgG would translate to 575 mg/dL and a 50% decrease from the low end of the normal range used for the inclusion criteria of 600 mg/dL in this study would be to 300 mg/dL. An 80% decrease from baseline after multiple doses would result in IgG levels of 230 mg/dL and 120 mg/dL, respectively. While these levels are in the range found in patients with primary humoral immunodeficiency ([Ameratunga et al., 2013](#)), the levels will be transient. Further, in other conditions, the temporary (ie, less than 4 months) depletion of IgG (up to 95% reduction of total IgG as seen with immunoadsorption) does not appear to impart an increased risk of infection ([Eming and Hertl, 2006](#); [Furst, 2009](#); [Keystone et al., 2007](#); [Schmaldienst et al., 2001](#); [van Vollenhoven et al., 2013](#)). Study subjects will be monitored clinically for any infection. Further, commercial IVIG can be given to immediately restore IgG levels in case of a bacterial infection occurring while their IgG levels are decreased.

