4.8.2 Pharmacodynamic / Disease Activity Analysis

PD samples will be collected for analyses throughout the study. PD samples will be collected according to the schedule shown in [Table 5](#).

Measurements for PD and disease activity biomarkers include:

- Total IgG assessments
- IgG subtypes (IgG1-4)
- Immunoglobulin A (IgA)
- Immunoglobulin M (IgM)
- Albumin levels
- CIC
- Hematocrit
- Hemoglobin
- Platelet count
- Reticulocyte count
- LDH
- Haptoglobin
- Direct Coombs tests
- Total and indirect bilirubin

PD/disease activity values, percentage change and absolute change from baseline will be summarized by cohort using descriptive statistics if result type is numerical. Mean (\pm SD) of values and percentage change and absolute change from baseline will be plotted by cohort. PD/disease activity result categories will be summarized if result type is categorical.

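### The secondary direct Coombs endpoint merges IgG and C3 into one result, so loss of red-cell IgG is scored as no change while C3 persists

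*Protocol*

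**What the plan says.** **Endpoint.** Under the secondary objective on disease markers, Protocol Section 3 states: "The direct Coombs test result (positive or negative) will be summarized by dose, dosing regimen and time point". SAP 2.1.2 repeats it. For the analysis, SAP 4.8.2 adds only a generic rule: "PD/disease activity result categories will be summarized if result type is categorical". Neither document plans a result by antiserum or a graded strength.

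**What makes the test positive.** Protocol Section 6.7.8: "Anti-IgG and anti-C3 antisera are added to a patient's red cells, and if IgG or C3 are present the RBCs clump or agglutinate". SAP 3.2.15 has the same description.

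**What the drug should do.** Protocol Section 2 expects SYNT001 to reduce the IgG on red cells. On antibody effects, Section 9.6.3 says: "These include acceleration of catabolism of IgG, but not other immunoglobulin isotypes such as IgA and IgM".

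**The other assay.** Protocol Section 6.7.9 describes the quantitative Coombs assay: "Subject and control RBC-bound IgG, IgM and C3 will be measured by flow cytometry". It is an exploratory endpoint in Section 3, and SAP 4.9.1 lists it among markers that the exploratory analysis may include, limited to data available at database lock.

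**The concern.** The endpoint is meant to show whether the drug changes the coating of red cells. The coating it is expected to reduce is IgG, but the recorded result stays positive for as long as either IgG or C3 is detectable. In a subject who carries both, complete loss of IgG leaves no trace in the endpoint unless C3 goes too.

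At stake is whether the result can be read. If most subjects stay positive, the table fits a drug that does nothing to red-cell IgG. It fits equally well a drug that removes the IgG and leaves C3 behind. Nothing in the planned direct Coombs summary tells these apart.

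**Working it through.** The plan states no rate for this endpoint, so there is no figure to reproduce. The check has three parts.

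**1. Possible changes, scored under the plan and by antiserum**

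| Baseline | Later visit | Planned result | Anti-IgG result |
|---|---|---|---|
| IgG only | none | positive to negative | positive to negative |
| IgG + C3 | none | positive to negative | positive to negative |
| IgG + C3 | C3 only | positive, unchanged | positive to negative |
| IgG + C3 | IgG + C3 | positive, unchanged | positive, unchanged |
| C3 only | none | positive to negative | negative, unchanged |

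Rows three and four get the same planned score, although the first is the effect sought and the second is not. Row five would count as a conversion with no change in IgG.

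**2. Size, under assumptions**

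Let r be the true rate of red-cell IgG loss, q the share of those subjects who also carry C3, and s the probability that C3 clears when IgG is lost. The documents give none of these.

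- Rate scored negative under the plan: r(1 − q) + r·q·s
- Rate scored negative by anti-IgG: r
- Share of IgG losses scored as still positive: 1 − [(1 − q) + q·s] = q(1 − s)

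| q | s = 0 | s = 0.5 |
|---|---|---|
| 0.25 | 0.25 × 1 = 25% | 0.25 × 0.5 = 12.5% |
| 0.50 | 0.50 × 1 = 50% | 0.50 × 0.5 = 25% |
| 0.75 | 0.75 × 1 = 75% | 0.75 × 0.5 = 37.5% |

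As counts, take the full 12 subjects of Cohort 2 and an assumed r of 50%, so 12 × 0.5 = 6 expected IgG losses. With s = 0 the planned endpoint would show 4.5, 3.0 or 1.5 conversions for q = 0.25, 0.50 or 0.75. With s = 0.5 it would show 5.25, 4.5 or 3.75. If q = 0 or s = 1, nothing is missed.

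**3. How far the quantitative assay covers the gap**

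Visits from Day 0, from Protocol Table 7 and SAP Table 6 (every-other-week schedule for Cohort 2):

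| | Direct Coombs | Quantitative Coombs | Direct test alone |
|---|---|---|---|
| Cohort 1 | Days 0, 14, 33, 56, 84, 112 | Days 0, 14, 33, 56 | Days 84, 112 |
| Cohort 2 | Days 0, 14, 28, 91, 140 | Days 0, 14, 28, 91 | Day 140 |

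At shared visits the quantitative assay can show IgG falling while C3 stays. In late follow-up, where any lasting effect would be looked for, the binary test is the only planned measure of red-cell coating. Section 6.7.9 gives IgG binding as a fluorescence intensity with no positivity cut-off, so the quantitative result does not by itself say who is IgG-positive.

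**The case against.** The strongest reply is that red-cell IgG is already measured, on a continuous scale, at most direct-test visits. SAP 4.9.1 provides summaries and plots of change for exploratory markers. The study is open-label and descriptive with a safety primary endpoint, so moving information from an exploratory to a secondary display alters no test or decision rule. This stands as a limit on the weight of the point. It does not remove it: the assay is optional in the SAP's wording, ends earlier than the direct test, and is not linked to the secondary endpoint.

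Three further points stand:

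- Protocol Section 6.7.8 describes C3 on the cell as a consequence of autoantibody binding. C3 may therefore clear as IgG falls, and s = 0 is the extreme case.
- The expected effect is a decrease in IgG coating, not necessarily its disappearance. A binary anti-IgG result would still miss a partial decrease.
- The documents do not say whether the laboratory already reads the two antisera separately, and the SAP's rule on result categories would not forbid reporting them. But neither document plans to.

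A reader might go further and infer that, because any positive test suffices for inclusion criterion 3, subjects with non-IgG disease enter and dilute the hemoglobin and hemolysis means. The documents do not support that step. The criterion reads "Confirmed diagnosis by enrolling physician of WAIHA, including positive direct Coombs test", so the test is one part of a physician's diagnosis of warm disease. Section 6.7.8 also says "WAIHA is caused by autoantibodies (usually IgG) that bind to RBC antigens" and places C3 deposition after that binding, so a C3-only result does not establish non-IgG disease. No explicit IgG requirement exists, but nothing shows how often such a subject would enter or that the drug would fail in that subject.

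**Conclusion.** The point holds for the secondary direct Coombs endpoint. As defined, it scores a change from IgG plus C3 to C3 alone as no change, so an unchanged result cannot be interpreted. This follows from the documents' own test description and endpoint definition and needs no outside figure.

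Its size does depend on assumptions. The share of IgG losses missed is q(1 − s), which runs from 12.5% to 75% over q = 25% to 75% and s = 0.5 to 0. The upper end requires that three quarters of subjects carry C3 and that it never clears.

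A reader might also infer that the trial cannot detect loss of red-cell IgG at all. That is too strong, because the quantitative assay can show it up to Day 56 in Cohort 1 and Day 91 in Cohort 2. The defect is confined to one descriptive secondary endpoint. It does not touch the safety objective or the sample size, and it does not call for a change to the entry criteria.

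**What to change.** In Protocol Sections 3 and 6.7.8 and SAP 2.1.2 and 4.8.2:

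1. Have the central laboratory report the anti-IgG and anti-C3 results of the direct Coombs test separately at every scheduled visit.
2. Define the Coombs endpoint as the anti-IgG result, positive or negative, by cohort and time point, with anti-C3 shown alongside.
3. At the shared visits, show the quantitative Coombs values for RBC-bound IgG and C3 in the same display, so that a partial decrease in IgG is visible.
4. Add a descriptive baseline classification of each subject as IgG, IgG + C3 or C3-only from the Day 0 data already collected, and state the rule used, since the quantitative assay has no cut-off in the documents.

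The cost is one more result field and one more display. No new sample or visit is needed, because both antisera are already part of the described procedure. Before adopting this, confirm with the laboratory whether the antisera are read separately now. If they are not, the change starts with the laboratory procedure, and results already obtained may exist only in combined form. Inclusion criterion 3 can stay as it is: changing it partway through enrolment could make later subjects differ from earlier ones and complicate the description by regimen.
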